4.3.4 Plan for optimizing recruitment and retention

At the time of enrollment, research assistants will collect information to facilitate multiple methods for contacting participants (phone, email, physical address) and will also obtain contact information for at least one caregiver, family member, or friend to use as a backup contact (VA medical records routinely include backup contact information). For each study visit after hospital discharge (see below), patients will receive an email and text reminder of their visit date 48 hours prior to the visit. Participants will also receive a \$20 gift card upon completion of each study visit, and a \$50 gift card if all visits are completed. To increase our likelihood of achieving the planned sample size, we will have weekly meetings via Microsoft Teams with graphical tracking of expected versus actual recruitment. We will also review the number of patients screened and reasons for non-enrollment of potential participants.

4.4 Randomization procedure

Randomized assignments will be generated ahead of time for each combination of strata and placed within stored and numbered envelopes kept at each hospital location. We will generate 20% more assignments than necessary to allow for potential withdrawals. Before patients are enrolled, physicians, patients, and research coordinators will not know which anesthesia modality will be assigned. Once patients are enrolled, the next envelope that applies to that participant (based on stratification factors) will be selected and labeled with the date and time of enrollment, the patient's name, and the research team member responsible for enrollment. The labeled and unopened envelope will be photographed for our records and the envelope number will be recorded in the participant's record.

Describe the method for identifying and recruiting candidates for the trial.

Describe procedures for documentation of reasons for ineligibility and for non-participation of eligible candidates (e.g. Screening Log).

Describe consent procedures, including any special requirements (e.g., consent for individuals who are unable to consent for themselves)

Describe the randomization procedure for assigning a participant to an intervention group.

5 STUDY INTERVENTIONS

5.1 Interventions, Administration, and Duration

5.1.1 Local Anesthesia

Patients in the local anesthesia arm will receive an injection of a 50:50 mix of 1% lidocaine with epinephrine and 0.25% Marcaine at the surgical site (in the skin and subcutaneous layers + beneath the external oblique aponeurosis). Patients in the local arm will also receive intravenous sedation (propofol or Precedex) and pain medication (morphine or fentanyl) at the discretion of the attending anesthesiologist.

5.1.1.1 Standardizing use of local anesthesia for participating surgeons

To ensure that patients receive local anesthesia in a consistent way, all participating surgeons will undergo a training session for the technique of local injection. This will consist of practicing injection with a 50:50 mix of 1% lidocaine with epinephrine and 0.25% Marcaine into the skin at the incision site and the subcutaneous tissue down to the external oblique aponeurosis. The technique for surgical repair will be a standard Lichtenstein operation with the choice of mesh depending on the surgeon's preference. To verify that the appropriate procedure for injection of local anesthesia is being followed, the principal investigator or research assistants will observe each surgeon's first five cases and provide feedback.

5.1.1.2 Collaboration with anesthesia providers during surgery:

We have worked closely with anesthesia providers at both sites to formulate protocols for sedation during surgery. Anesthesia providers will refrain from using benzodiazepines prior to or during surgery given the known cognitive effects of that medication class on older adults. We will not otherwise mandate use of any particular agents for sedation or pain control, but expressed our preference for using propofol and fentanyl because of their short half-lives and limited side effect profile for older adults.

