5.2 Handling of Study Interventions

The medications necessary for administration of local and general anesthesia are available at the hospital from our pharmacy as part of routine care. Local anesthesia will be prepared by the surgical circulating nurse (not a member of the research team) in the operating room as is routinely done for clinical practice outside this trial.

The research assistants will be blinded to study allocation, as they will not be present during the operation and will only interact with patients before and after the operation. Due to the use of some IV medication (propofol or Precedex) for patients in the local arm, it will not necessarily be obvious postoperatively whether the patient had surgery under local or general anesthesia. Additionally, the incisions will be the same regardless of study arm and postoperative care will be identical.

Adverse reactions to any medications intraoperatively will be managed as described below.

For studies involving drugs and dietary or nutritional supplements, describe how these are to be acquired by the participating clinical sites (e.g., the pharmaceutical company will distribute the drug in bulk to the site pharmacist), and how they are to be stored, prepared, dispensed and, if applicable, how unused study products are destroyed or to be returned to the company supplying them.

Provide instructions for completing study intervention accountability records. If appropriate, reference the study Manual of Operations for detailed instructions on these issues.

For lifestyle/behavioral interventions, describe the intervention and general approach for delivering the intervention (e.g., manual describing procedures).

Note mechanisms (if any) for masking (i.e., blinding) study interventions. For example, if a placebo is being used in a drug trial, note whether it has similar color, taste, etc., as the active drug.

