10.3 Quality Assurance

10.3.1 Training

10.3.1.1 Surgeon training in use of local anesthesia

All participating surgeons will undergo training in the injection of local anesthesia for inguinal hernia repair. The training will consist of either in person or video training with the principal investigator serving as instructor. Instruction will consist of two parts: a slideshow demonstrating pictures of the technique and practice performing the injection. For the practice session, a chicken breast purchased from a local grocery store will serve as the practice site for injection. Under supervision of the principal investigator, the participant and surgeon will first mark a practice “incision” on the chicken and inject the “skin” with 10 mL of the local anesthesia mix, using a 10cc syringe. The surgeon will then hub the syringe to practice injecting the deep tissue and fascia along the length of the incision. To verify application of the above training and practice, the principal investigator will observe (either in person or by video) the first operation under local anesthesia by each surgeon.

A brief training session will be repeated after the first six months to reinforce study protocols.

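### The surgeon training omits an injection layer that the local-anesthesia definition includes, and the observation rules conflict with each other and with the blinding plan

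*Combined protocol and SAP*

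**What the plan says.** **Technique.** Section 5.1.1 states what local-arm patients receive: the lidocaine and Marcaine mix at the surgical site, "in the skin and subcutaneous layers + beneath the external oblique aponeurosis". Section 5.1.1.1, whose stated aim is consistent delivery, has all participating surgeons practise injecting the same mix "into the skin at the incision site and the subcutaneous tissue down to the external oblique aponeurosis". Section 10.3.1.1 describes the training as a slideshow followed by practice on a chicken breast: 10 mL into the simulated skin, then "injecting the deep tissue and fascia along the length of the incision".

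**Observation.** Section 5.1.1.1 says that "the principal investigator or research assistants will observe each surgeon's first five cases and provide feedback". Section 10.3.1.1 says that "the principal investigator will observe (either in person or by video) the first operation under local anesthesia by each surgeon".

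**Blinding.** Section 5.2 explains that research assistants are blinded because "they will not be present during the operation and will only interact with patients before and after the operation". The section on masking treatment assignment (the second one numbered 9.2.1) says that the investigative team stays blinded throughout, that only the statistician is excepted until the analysis is complete, and that the assistants collecting perioperative and postoperative outcomes are blinded.

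**Other checks.** Section 5.4 reviews operative and anesthesia records for the type of anesthesia given and for conversion, and has assistants ask surgeons about deviations at the end of each operative day. The Visit 2 data in 6.2.3 include the dose of local anesthesia.

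**The concern.** The local-anesthesia technique is the intervention under test, and trying out procedures before a multisite trial is a main purpose of this pilot. If the text that standardizes the technique leaves out a layer that the definition includes, a surgeon who follows the training text to the letter has not been trained in the full definition. The check meant to catch this has two unlinked rules that differ in number of operations and in observer. An investigator reporting fidelity would have to choose which rule applied.

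The observer conflict has a more direct consequence. Anyone who watches an operation learns the arm. If that person later administers the cognitive, pain or quality-of-life instruments to the same participant, the assessment is no longer blind, and assessor blinding is the only masking of outcome measurement that the plan offers.

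**Working it through.** The main check is a comparison of text; the plan gives no figure to reproduce.

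**1. Injection layers**

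| Section | Purpose of the text | Skin and subcutaneous | Beneath the aponeurosis |
|---|---|---|---|
| 5.1.1 | Delivery to patients | Yes | Yes |
| 5.1.1.1 | Training for consistent delivery | Yes, down to the aponeurosis | Not mentioned |
| 10.3.1.1 | Practice exercise | Skin, then deep tissue and fascia | Not named |

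Only 5.1.1 is an instruction on what patients receive. The gap therefore lies between the delivery definition and the training meant to standardize it. Neither training section names the layer beneath the aponeurosis.

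**2. Observation rule**

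| Section | Number per surgeon | Observer | What is counted |
|---|---|---|---|
| 5.1.1.1 | Five | Principal investigator or research assistants | Cases |
| 10.3.1.1 | One | Principal investigator, in person or by video | Operations under local anesthesia |

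Both can be met at once: the principal investigator attends the first local-anesthesia operation and either observer attends the rest of the five. Nothing in the text links them, however, and a surgeon checked under 10.3.1.1 alone would fall short of 5.1.1.1.

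**3. Observer against blinding**

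- Research assistants: 5.1.1.1 allows them to watch operations; 5.2 says they are not there and gives that as the reason they are blinded. The two statements cannot both hold.
- Principal investigator: both training sections have this person watching local-anesthesia operations; the masking section excepts only the statistician. Observation by video reveals the arm just as well.

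**4. Scale (illustrative)**

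Inputs: 40 local-arm operations (3.1 and 9.2.1); S surgeons, not given in the documents and assumed to be 4 to 8; each surgeon performs at least five local-arm operations, also assumed.

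Coverage = S × (operations observed per surgeon) / 40.

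- One each: 4 × 1/40 = 10%; 8 × 1/40 = 20%.
- Five each: 4 × 5/40 = 50%; 8 × 5/40 = 100%.

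The same counts, 4-8 against 20-40 participants, are the numbers whose allocation an observer would learn.

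**5. Do other checks fill the gap?** The record review in 5.4 names type of anesthesia and conversion, and Visit 2 records dose. No listed item records which layers were injected.

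**The case against.** The strongest reply is that there is one delivery instruction, in 5.1.1, and that deviations from it are collected for every case under 5.4 and counted under 10.3.3. One instructor, the principal investigator, trains all surgeons, with a repeat session after six months, and the slideshow may well show the full technique. The two observation rules are compatible. On blinding, the masking section has one assistant open the envelope after baseline and a different one carry out later assessments, so an assistant who already knows the arm could observe without rating outcomes.

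Much of this stands, and it rules out several stronger readings:

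- A reader might see three competing techniques and take the 10 mL as an intervention volume. That volume belongs to the chicken-breast exercise, and the deep-tissue wording is general rather than contradictory.
- A reader might infer that the two sites will deliver different interventions. No site-specific technique appears, and the shared instructor argues against it.
- A reader might take the five cases to include general-anesthesia operations. The sentence is about verifying local injection, so local-anesthesia cases are the natural reading.
- A reader might reason that a shallower injection leads to more sedation, opioid or conversion. The documents do not say so.

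What does not stand is the inference that nothing needs changing. Section 5.1.1.1 does not restrict observation to assistants who are already unblinded, and 5.2 keeps all of them out of the operating room. A deviation in layers is also hard to count when the training text omits one of them and no form records them.

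**Conclusion.** The point holds as a set of inconsistencies to be reconciled. The training text is narrower than the intervention definition. The two observation rules differ in number and observer and are not linked. Both observer options conflict with the blinding statements. The observer conflict matters most, because following 5.1.1.1 literally puts blinded staff in the operating room.

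No effect on the feasibility outcomes or the exploratory arm comparisons can be derived from the documents. The coverage contrast of 10-20% against 50-100% rests on the assumed number of surgeons and on at least five local-arm operations per surgeon; it shows only that the choice of rule is not trivial. A breach of blinding depends on an observing assistant later rating the same participant, which the text permits but does not require. Nothing here says which injection technique is right; that is for the investigators.

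**What to change.** - Reconcile 5.1.1, 5.1.1.1 and 10.3.1.1 to a single description of the injection layers, chosen by the investigators, and use it in the slides and the practice session.
- State one observation rule in both training sections, counted in local-anesthesia operations per surgeon.
- Name an observer role that does not rate outcomes. Remove outcome-rating research assistants from it, so that 5.1.1.1 agrees with 5.2.
- Amend the masking section, and the matching statement in the Précis, to acknowledge any investigator unblinded by observing operations.
- Add the layers injected to the Visit 2 operative data, next to the dose already recorded, so that technique can be reported for all 40 local-arm operations.

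The cost is protocol and slide wording and one line on a form. Observation time depends on the number chosen: 4-8 operations at one per surgeon or 20-40 at five, under the assumed 4 to 8 surgeons. One of the two sections already commits to each. If assistants no longer share the task, that time falls on the principal investigator or another person who rates no outcomes.

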5.1.2 General anesthesia

General anesthesia will be administered at the discretion of the anesthesiologist and will involve a combination of inhaled and intravenous anesthesia.

5.1.3 Surgical technique

Open surgical repair will utilize the Lichtenstein tension-free repair with mesh. Choice of mesh will be at the discretion of the attending surgeon.

Indicate each study intervention, including how it is administered and the dosing schedule, as well as potential adverse effects. Indicate where the intervention will be administered (e.g., outpatient, exercise laboratory, intensive care unit). State guidelines for use of appropriate supportive care, medications or treatments.

Describe dose escalation procedures if relevant.

Include instructions for modifications to the study interventions, if appropriate and clearly explain modification of dose due to toxicity or any other reason. Address dose modifications for specific abnormal laboratory values of concern or other adverse events that are known to be associated with the planned intervention regimen.

For drug studies, package insert information can be referred to, but does not need to be included unless there is a new, significant change. Justify any aspects of the study that are not FDA-approved (e.g., different dosing schedule, new combination of drugs, new drug formulation).

5.2 Handling of Study Interventions

The medications necessary for administration of local and general anesthesia are available at the hospital from our pharmacy as part of routine care. Local anesthesia will be prepared by the surgical circulating nurse (not a member of the research team) in the operating room as is routinely done for clinical practice outside this trial.

The research assistants will be blinded to study allocation, as they will not be present during the operation and will only interact with patients before and after the operation. Due to the use of some IV medication (propofol or Precedex) for patients in the local arm, it will not necessarily be obvious postoperatively whether the patient had surgery under local or general anesthesia. Additionally, the incisions will be the same regardless of study arm and postoperative care will be identical.

Adverse reactions to any medications intraoperatively will be managed as described below.

For studies involving drugs and dietary or nutritional supplements, describe how these are to be acquired by the participating clinical sites (e.g., the pharmaceutical company will distribute the drug in bulk to the site pharmacist), and how they are to be stored, prepared, dispensed and, if applicable, how unused study products are destroyed or to be returned to the company supplying them.

Provide instructions for completing study intervention accountability records. If appropriate, reference the study Manual of Operations for detailed instructions on these issues.

For lifestyle/behavioral interventions, describe the intervention and general approach for delivering the intervention (e.g., manual describing procedures).

Note mechanisms (if any) for masking (i.e., blinding) study interventions. For example, if a placebo is being used in a drug trial, note whether it has similar color, taste, etc., as the active drug.

